## 11.1. Definition of Adverse Events

An AE is any untoward medical occurrence in a participant or clinical investigation participant, temporally associated with the use of a medicinal product, whether or not considered related to the medicinal product.

An AE can therefore be any unfavorable and unintended sign (including an abnormal laboratory finding), symptom, or disease (new or exacerbated) temporally associated with the use of a medicinal product.

Events meeting the definition of an AE **include but are not limited to**:

- Any clinically significant, new or worsened, abnormal laboratory test results (hematology, clinical chemistry, or urinalysis) or other safety assessments (e.g., ECGs, radiological scans, vital signs measurements). Clinical significance is determined based on the medical and scientific judgement of the Investigator.
- Exacerbation of a chronic or intermittent pre-existing condition including an increase in frequency and/or intensity of the condition.
- Signs, symptoms, or the clinical sequelae of a suspected interaction (e.g. with medications or food).
- Signs, symptoms, or the clinical sequelae of a overdose of either investigational product or a concomitant medication (overdose without an AE should be reported as a protocol deviation).

Events that **do not** meet the definition of an AE include:

- Anticipated day-to-day fluctuations of pre-existing condition(s), including the disease under study, that do not represent a clinically significant exacerbation or worsening.
- Abnormal or worsening laboratory, imaging, or other safety findings that are not clinically significant.
- Medical or surgical procedures (e.g., endoscopy, appendectomy); the condition that leads to the procedure is an AE.
- Situations where an untoward medical occurrence did not occur (social and/or convenience admission to a hospital).

## 11.2. Definition and Reporting of Serious Adverse Events

Serious adverse events must be marked as a SAE within the AE eCRF form, which will send an immediate auto notification to [REDACTED] and the Medical Monitor.

If the eCRF is not available, the site must email [REDACTED] and the Medical Monitor within 24 hours of the study site personnel's knowledge of the event.

A SAE is any untoward medical occurrence that, at any dose:

- Results in death
- Is life-threatening

The term 'life-threatening' in the definition of 'serious' refers to an event in which the participant was at risk of death at the time of the event. It does not refer to an event, which hypothetically might have caused death, if it were more severe.

- Requires hospitalization or prolongation of existing hospitalization

Hospitalization planned prior to signing the informed consent is not considered an SAE. Surgeries and other interventions that were under consideration prior to signing the informed consent are not considered an SAE if the underlying condition has not changed from baseline.

“Hospitalization” includes admission to the hospital of any duration. It does not include emergency room visits. Complications that occur during hospitalization are AEs and are SAEs if they prolong hospitalization or fulfill any other serious criteria.

Hospitalization for elective treatment of a pre-existing condition that did not worsen from baseline is not considered an AE.

- Results in disability/incapacity

The term disability means a substantial disruption of a person's ability to conduct normal life functions. This definition is not intended to include experiences of relatively minor medical significance such as uncomplicated headache, nausea, vomiting, diarrhea, influenza, and accidental trauma (e.g. sprained ankle) which may interfere or prevent everyday life functions but do not constitute a substantial disruption.

- Is a congenital anomaly/birth defect
- Is an important medical event that may jeopardize the subject or may require medical or surgical intervention to prevent one of the other outcomes listed in the above definition. Examples of such events are allergic bronchospasm, blood dyscrasias or convulsions where treatment prevents the need for hospitalization.

The following should always be considered serious: invasive or malignant cancers, and development of drug dependency or drug abuse.

### **11.3. Time Period and Frequency for Collecting AE and SAE Information**

- AEs will be collected from the time of informed consent until the follow-up contact, at the timepoints specified in the Section 8.1 and 8.2, Time and Events Tables.
- Medical occurrences that begin prior to any study procedure but after obtaining informed consent may be recorded on the Medical History/Current Medical Conditions section of the eCRF.
- All SAEs will be recorded and reported to the Sponsor within 24 hours of site awareness.
- Any SAEs assessed as related to study participation (e.g., protocol-mandated procedures, invasive tests, or change in existing therapy) or related to investigational

product will be recorded from the time a participant consents to participate in the study up to and including any follow-up contact.

- Once former study participants have completed the study, the Principal Investigator is not obligated to actively seek AEs or SAEs. However, if the Principal Investigator learns of any SAE, including a death, at any time after a participant has been discharged from the study, and he/she considers the event reasonably related to the investigational product or study participation, the Principal Investigator must promptly notify the Sponsor.

#### **11.4. Method of Detecting and Reporting AEs and SAEs**

Care will be taken not to introduce bias when detecting AEs and/or SAEs. Open-ended and non-leading verbal questioning of the participant is the preferred method to inquire about AE occurrence. Appropriate questions include:

- “How are you feeling?”
- “Have you had any (other) medical problems since your last visit/contact?”
- “Have you taken any new medicines, other than those provided in this study, since your last visit/contact?”

All AEs and SAEs should be promptly recorded in the eCRF, completing all fields for which data is available. When known, the diagnosis should be entered as the event term in the eCRF, rather than individual symptoms. When the diagnosis is unclear, key symptoms may be entered, and the investigator should obtain appropriate tests to establish a diagnosis, if possible. Discharge summaries should be requested for all hospitalizations.

For SAEs, the eCRF will send an auto notification to

[REDACTED] and the Medical Monitor when the form is saved. Each SAE should be assigned a causality at the time of entry, as this is required to determine regulatory reporting. Follow-up information regarding the SAE, including hospital discharge summary, should be emailed to  
[REDACTED]

#### **11.5. Assessing Severity of AEs and SAEs**

Severity describes the intensity of a specific event (as in mild, moderate, or severe myocardial infarction); the event itself, however, may be of relatively minor medical significance, such as a severe headache. This is not the same as “serious,” which is based on participant/event outcome or action taken.

The Investigator must determine the severity of each AE according to the following criteria:

### Criteria for Determining the Grade/Severity of Adverse Event Terms

Grade	Criteria
1/Mild	Asymptomatic or mild symptoms, clinical or diagnostic observations only; intervention not indicated
2/Moderate	Minimal, local, or noninvasive intervention indicated; limiting age-appropriate instrumental activities of daily living
3/Severe or medically significant	Not immediately life-threatening; hospitalization or prolongation of hospitalization indicated; disabling; limiting self-care activities of daily living
4/Life-threatening	Life threatening consequences; urgent intervention indicated
5/Death	Death related to adverse event

Adverse event severity should be recorded in the appropriate section of the AE eCRF and in the participant's source documents.

### 11.6. Assessing Causality of AEs and SAEs

Regulatory authorities require that both investigator and sponsor assess whether there is a reasonable possibility that the study treatment caused each AE. This assessment requires careful medical consideration of each event in relationship to the timing of drug administration, the presence of other factors which may have caused the event (underlying illness, concomitant medication, complications, exposure to other toxins or allergens, environmental factors, etc.), and the effects of stopping and/or restarting the study treatment. The following definitions are to be used for the relationship of the AE to Study Treatment:

The investigator will assess the causality of each reported AE as follows:

- Probably related: an AE occurring at a reasonable time following administration of a drug, where other causes are unlikely, there is evidence to suggest that the drug caused the event, and/or where the event recurs after reintroduction of the drug (without other explanation for the recurrence).
- Possibly related: an AE occurring at a reasonable time following administration of a drug and for which there is a reasonable possibility that the drug caused the event, e.g. there is some evidence to suggest a causal relationship.
- Not related: an AE with poor or no relationship to the timing of drug administration, or where another cause such as underlying disease, complications, or other medications reasonably explains the event, or where the event does not recur after continued administration or reintroduction of the drug for an adequate period.

## **11.7. Follow-up of AEs and SAEs**

After the initial AE/SAE report, the Principal Investigator is required to proactively follow each event at subsequent visits/contacts until the event resolves. All SAEs and AEs will be followed until resolution, or until the condition stabilizes or until the participant is lost to follow-up. Where necessary, repeated laboratory testing should be requested to confirm resolution. Ongoing AEs where no further information is likely to be available may be closed after consultation between the Sponsor and Medical Monitor.

## **11.8. Regulatory Reporting Requirements for SAEs**

Prompt notification by the Investigator to the Sponsor of SAEs/adverse event of special interest (AESIs) is essential so that legal obligations and ethical responsibilities towards the safety of subjects and the safety of a product under clinical investigation are met.

The Sponsor has a legal responsibility to notify both the local regulatory authority and other regulatory agencies about the safety of a product under clinical investigation. The Sponsor will comply with country specific regulatory requirements relating to safety reporting to the regulatory authority, IRB/IEC and Investigator.

Investigator safety reports are prepared for suspected unexpected serious adverse reactions (SUSARs) according to local regulatory requirements and are forwarded to the Investigators in accordance with local regulations.

The Investigator who receives an Investigator safety report describing a SAE(s)/AESI(s) or other specific safety information (e.g., summary or listing of SAEs) from the Sponsor will file it with the IB and will notify the IRB/IEC, as appropriate according to local requirements.

## **11.9. Overdose**

Overdose is less likely in a study where the drug is administered within a clinical unit by a healthcare provider. If there are no symptoms of an overdose, it may be recorded as a protocol deviation. Overdose with symptoms should be recorded as an AE or SAE, as appropriate.

## **12. PREGNANCY REPORTING**

All female participants will be tested for pregnancy prior to study drug dosing. Participants testing positive for pregnancy will be ineligible for study participation.

Any pregnancies in a subject, or the partner of a subject, between the time of informed consent and study termination must be reported to the Sponsor within 24 hours of learning of the pregnancy. Information on the status and health of the mother, the pregnancy and its outcome, and the child will be recorded on the form provided. In case of a partner pregnancy, the partner of the study subject will be asked to sign a partner

pregnancy consent form in order to collect pregnancy and outcome information. Information on the status of the mother and child will be forwarded to the Sponsor. Generally, follow-up will be no longer than 6 to 8 weeks following the estimated delivery date. Any premature termination of the pregnancy will be reported.

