### **Open-Label Extension**

If the participant is eligible and consents to enroll into the OLE, starting at Week 8 an additional 3 doses of 340 mg RVT-1401 will be administered over a 6-week period (every 2 weeks) followed by a 6-week follow up period.

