  - b. Child-bearing potential and agrees to use one of the contraception methods listed in Section 6.6.1 for an appropriate period of time (as determined by the product label or Principal Investigator) prior to the start of dosing to sufficiently minimize the risk of pregnancy at that point. Female participants must agree to use contraception until 90 days after the last dose of study treatment.
7. Male participants must agree to use one of the contraception methods listed in Section 6.6.1. This criterion must be followed from the time of the first dose of study treatment until 90 days after the last dose of study treatment.
8. Willing and capable of giving written informed consent, which includes compliance with the requirements and restrictions listed in the consent form.

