###### **Contraceptive Methods with a Failure Rate of <1%**

- Combined hormonal contraception associated with inhibition of ovulation (oral, intravaginal, transdermal).
- Progestogen-only hormonal contraception associated with inhibition of ovulation (oral, injectable, implantable).
- Intrauterine device (IUD) or intrauterine system (IUS) that meets the <1% failure rate as stated in the product label.

- Male partner sterilization (vasectomy with documentation of azoospermia) prior to the female participant's entry into the study, and this male is the sole partner for that participant. For this definition, “documented” refers to the outcome of the investigator's/designee's medical examination of the participant or review of the participant's medical history for study eligibility, as obtained via a verbal interview with the participant or from the participant's medical records.
- Female participants and female partners of male study participants using a hormonal contraceptive must also use a barrier method (i.e., condom or occlusive cap [diaphragm or cervical/vault caps]) and should have been stable on their hormonal contraceptive treatment for at least 4 weeks before Screening.
- Sterilized male participants who have had vasectomy with documented azoospermia post procedure can be included.
- Non-sterilized male participants who are sexually active with a female partner of childbearing potential must use effective method of double barrier contraception. Male participants practicing true sexual abstinence (when this is in line with the preferred and usual lifestyle of the participant) can be included. In addition, male participants must be advised not to donate sperm during this period from signing of Informed Consent Form (ICF), throughout the duration of the study, and for 90 days after the last administration of study drug.

These allowed methods of contraception are only effective when used consistently, correctly and in accordance with the product label. The investigator is responsible for ensuring participants understand how to properly use these methods of contraception.

Participants must be completely informed of the unknown risks of pregnancy and agree not to become pregnant during the time they are participating in this study. If there is any question that a participant will not be reliable in the use of appropriate contraceptive methods, they should not be entered into the study.

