Injection site reactions 			X			X	X	X	X				X		X	X					
MG-ADL 			X			X	X	X	X			X	X		X	X			X	X	
Quantitative Myasthenia Gravis (QMG) Score 	X	X			X	X	X	X				X	X		X	X			X	X	

	Screening 	Treatment Period Week 1 (Days)			Treatment Period Weekly Visit (Weeks)				Treatment Period Week 6 (Days)			OLE and Follow-up Period Weekly Visit (Weeks)							Early Withdrawal Visit	
		Day 1 (Baseline)	Day 3	Day 5	2 (Day 8)	3 (Day 15)	4 (Day 22)	5 (Day 29)	6 (Day 36)	Day 38	Day 40	7	8	9	10	12	14	16	18	
Study Timepoint (Weeks)	Within 21 Days																			
Time Window (days)			+1 day	+1 day	+/-1 day	+/-1 day	+/-1 day	+/-1 day	+/-1 day	+1 day	+1 day					+/-2 days	+/-2 days	+/-2 days	+/-2 days	+/-2 days
Myasthenia Gravis Composite (MGC) Score 		X			X	X	X	X				X	X			X	X			X
Myasthenia Gravis Quality of Life (MG- QOL15r) Score 		X						X								X	X			X
Satisfaction Questionnaire												X								X
Adverse events	X	X	X	X	X	X	X	X	X	X	X	X	X	X	X	X	X	X	X	
Concomitant medication	X	X	X	X	X	X	X	X	X	X	X	X	X	X	X	X	X	X	X	

1. Screening can take place over multiple days to ensure participants withhold cholinesterase inhibitors for at least 12 hours prior to the QMG and MGC assessments.
2. Consent for enrollment into the OLE must occur prior to Week 8.
3. Participants who complete the 6-week, randomized, double-blind treatment phase are eligible to participate in the OLE
4. Vitals, ECG and blood draws for safety, PK, and PD assessment will be collected pre-dose on dosing days where specified.
5. Pregnancy tests will be collected pre-dose (via urine dipstick) on dosing days where specified. Serum pregnancy tests should be collected at screening, week 18, and early withdrawal.
6. Participants positive for anti- RVT-1401 antibody at Week 18 will be requested to return at approximately 6, 9, and 12 months post-dose for additional samples or until their result is no longer positive. However, for purposes of safety follow-up and database lock participation ends at the Week 18 visit.
7. Local injection site reactions will be assessed at approximately 10 minutes post dose.
8. MG assessments will be assessed pre-dose when collected on dosing days.
9. Subjects should be instructed to withhold cholinesterase inhibitors for at least 12 hours prior to the QMG and MGC assessments.

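### Required pregnancy reporting stops at an undefined study termination, which can fall short of the protocol's own 90-day post-dose window: by 48 days for an OLE completer if it means the Week 18 visit

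*Protocol*

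**What the plan says.** **Contraception and related restrictions.** In Protocol Section 6.2, criterion 6b covers women of childbearing potential: "Female participants must agree to use contraception until 90 days after the last dose of study treatment". Criterion 7 covers men: "This criterion must be followed from the time of the first dose of study treatment until 90 days after the last dose of study treatment". Section 6.7.1 also bars men from donating sperm during the study and "for 90 days after the last administration of study drug".

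**Reporting.** Section 12 covers pregnancies in participants and in their partners. It requires notification for those "between the time of informed consent and study termination must be reported to the Sponsor within 24 hours of learning of the pregnancy". It then provides for outcome follow-up, generally to 6 to 8 weeks after the estimated delivery date. It does not say what study termination means.

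**Calendar.** Section 5.1 gives three OLE doses at two-week intervals from Week 8, "followed by a 6-week follow up period". Participants who decline the OLE have 12 weeks of follow-up after the Week 6 dose. Overall study duration is the same on both routes. A footnote to the Time and Events Tables (Sections 8.1 and 8.2) states that "for purposes of safety follow-up and database lock participation ends at the Week 18 visit". The last scheduled pregnancy test is the serum test at Week 18 or at early withdrawal.

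**After completion.** Section 11.3 states: "Once former study participants have completed the study, the Principal Investigator is not obligated to actively seek AEs or SAEs". An SAE that the investigator learns of later, and considers related to the product or to participation, must still be notified. Section 11.2 lists a congenital anomaly as an SAE. It does not list pregnancy as such.

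**The concern.** By its own criteria, the protocol treats the 90 days after the last dose as a period in which conception should be avoided. Section 12 does not tie reporting to those 90 days. Its end point is a separate, undefined event that can come well before Day 90. The contraception section itself describes the risks of pregnancy as unknown, so the few pregnancies that might occur would be informative.

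Two things are at stake. One is the duty to report, which depends on what study termination is taken to mean. The other is detection: even where a duty exists, someone has to learn of the pregnancy, and nothing is scheduled after Week 18 for that purpose. Partners are not tested at any visit, so a partner pregnancy comes to light only if somebody mentions it. A pregnancy that is never reported does not enter the outcome follow-up that Section 12 sets up.

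**Working it through.** **Inputs**

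- Day labels: the Time and Events Tables equate Week 2 with Day 8 and Week 6 with Day 36, so Week *w* = Day 1 + 7(*w* − 1).
- Last OLE dose: Weeks 8, 10 and 12, so Week 12 = Day 1 + 7 × 11 = Day 78.
- Last double-blind dose: Week 6 = Day 36.
- Last visit and last pregnancy test: Week 18 = Day 1 + 7 × 17 = Day 120.
- Contraception window: 90 days after the last dose.
- Visit windows: ±1 day at Week 6, ±2 days at Weeks 12 and 18.
- I take Section 12 to apply to a pregnancy that begins within its period. One that begins before the end point but is noticed afterwards is assumed to remain reportable.

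**Reproducing the plan's own figures**

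- OLE follow-up: 120 − 78 = 42 days = 6 weeks, as stated.
- Follow-up without OLE: 120 − 36 = 84 days = 12 weeks, as stated.

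**Reading A: study termination is the participant's own last visit**

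| Route | Last dose | Last visit | Days covered | End of 90 days | Gap |
|---|---|---|---|---|---|
| OLE, Week 12 dose given | Day 78 | Day 120 | 42 | 78 + 90 = Day 168 | 168 − 120 = 48 days |
| No OLE | Day 36 | Day 120 | 84 | 36 + 90 = Day 126 | 126 − 120 = 6 days |

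- As a share of the window, the OLE gap is 48/90 = 53%.
- OLE with visit windows: coverage is 42 ± 4 = 38 to 46 days, so the gap is 44 to 52 days.
- No OLE with visit windows: coverage is 84 ± 3 = 81 to 87 days, so the gap is 3 to 9 days.
- Early withdrawal: the gap is 90 minus the days from last dose to the early termination visit. For illustration, a visit 7 days after the last dose leaves 90 − 7 = 83 days.

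**Reading B: study termination is the end of the trial** (Section 6.11: the last visit of the last participant)

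Let *g* be the number of days between a participant's own Week 18 visit and the last participant's last visit.

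- OLE: gap = max(0, 48 − *g*). It is 48 days when *g* = 0 and nil once *g* reaches 48.
- No OLE: gap = max(0, 6 − *g*).
- Early withdrawers are also covered until the trial ends.

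**Detection, on either reading**

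The schedules contain no pregnancy test, visit or call between Week 18 (or early withdrawal) and the end of the 90 days. The return visits requested of antibody-positive participants come at about 6, 9 and 12 months post-dose, are for antibody samples, and concern only that subset.

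**Scale of expected events**

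Section 6.7.1 requires women of childbearing potential to be abstinent or to use a method with a pregnancy rate below 1% per year. Assume, for illustration only, a 1% rate for all 21 participants, all of them completing the OLE: 21 × 48/365 × 0.01 = 0.03 pregnancies. No rate is given for partners of male participants, so this shows the order of magnitude and is not an upper bound.

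**The case against.** The strongest objection concerns the meaning of study termination. Section 6.11 defines the end of the study at trial level, Section 13.1.1 dates study completion by the last participant, and Section 13.3.3 speaks of terminating the whole study. On that usage most participants would have a shorter gap or none. This stands, and it means the 48 days cannot be given as the reporting gap for every OLE participant. It does not remove the problem. The footnote that ends participation at Week 18 points the other way, Section 12 does not choose between the two, and under the trial-level reading a participant's cover depends on enrolment order.

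A reader might also infer that pregnancies in the gap are not collected at all. The documents do not support that. Section 12 sets a duty and does not bar a later report, and a related SAE such as a congenital anomaly would still have to be notified if the investigator learned of it. The sentence in Section 11.3 about not actively seeking events concerns AEs and SAEs, so it should not be read as a rule on pregnancies. What can be said is that reporting is not clearly required and that no contact is planned.

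Third, the protocol does not explain the 90 days. Section 3.2.2 expects IgG to be back at baseline 6 to 8 weeks after OLE dosing, that is 42 to 56 days, so a conception late in the gap may involve little or no remaining drug effect. A precautionary contraception period and a reporting period need not be identical. This is fair and limits the weight of the point. Even so, reporting under Reading A can stop at the lower end of that recovery range.

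Finally, the consent form, the pregnancy form and the study reference manual were not available to this review. Any of them might contain a later reporting instruction.

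**Conclusion.** The mismatch holds. The contraception and sperm-donation provisions run to 90 days after the last dose, while required pregnancy reporting runs to an undefined point. Under the per-participant reading the gap is 48 of 90 days after a Week 12 OLE dose (44 to 52 with windows) and about 6 days without the OLE (3 to 9). Early withdrawers can have a longer gap. Under the trial-level reading the full 48 days apply only to an OLE participant who finishes last. The detection gap is the same on both readings, because nothing is scheduled after Week 18 or early withdrawal.

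Two stronger conclusions are not supported. One is that each conception in the gap is a lost drug exposure: the documents do not establish exposure out to Day 90. The other is that the reporting window was overlooked when the OLE was added: the text available shows only the current wording and not how it came about.

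The practical weight is modest. About 21 participants are planned, only some fall under the criterion, and the expected number of events is small. The change is worth making because it is cheap and improves safety capture on either reading.

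**What to change.** 1. In Section 12, state that pregnancies in participants, including early withdrawers, and in partners are reportable until study termination or 90 days after the last dose of study treatment, whichever is later.
2. Define study termination in Section 12, saying whether it refers to the participant's last visit or to the end of the trial as in Section 6.11.
3. Add one telephone contact at about 90 days after the last dose for participants to whom criterion 6b or 7 applies, including those who withdrew early.

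The reporting period would then run to Day 168 for a participant with a Week 12 OLE dose. Without the OLE it would run to Day 126, in each case or to study termination if that is later. The contraception period does not change.

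The cost is a short protocol and consent-form amendment and a few telephone calls after Week 18. Those calls would be handled outside the database lock. The protocol already does this for antibody follow-up, since participants positive at Week 18 are asked to return up to 12 months post-dose although participation has formally ended.
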